3.3.3 Secondary Safety Outcomes

Bleeding Complications

Bleeding complications are a composite endpoint previously defined in the literature that includes, 1) symptomatic bleeding into a critical area or organ, 2) bleeding causing a drop in hemoglobin level of 2 g/dL or more over a 24-hour period, or leading to transfusion of two or more units of whole blood or red cells or; 3) bleeding requiring reoperation.

Wound Complications

Wound complications include wound drainage, hematoma, or seroma of an orthopaedic injury that requires a subsequent surgery.

Deep Surgical Site Infection

Deep surgical site infection is defined based on the Centers for Disease Control and Prevention’s National Healthcare Safety Network criteria for deep or organ space infections at the fracture site and requires surgical treatment.

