2.3 Potential Risks and Benefits

2.3.1 Potential Risks The risks associated with participation in this study are primarily the risks that are associated with each of the study drugs.

Patients randomized to the LMWH arm would have no drug-related risk over and above the risk they would experience as standard of care. These risks include bruising or infection at the site of injection and allergic reaction, ranging from hives and itching to difficulty breathing or throat swelling. Some participants may experience Heparin Induced Thrombocytopenia, which results in a reduced number of platelets and hypercoagulability. Risks associated with the LMWH arm also include bleeding complications, which could require transfusion or operation, and kidney damage.

Patients randomized to the aspirin arm would have no drug-related risk over and above the risk they would experience as using aspirin for blood clot prevention. These risks include the potential to experience the risks associated with aspirin, including possible risk of inflammation or ulceration of the stomach, allergic reaction (ranging from hives and itching to difficulty breathing or throat swelling), ringing of the ears, and worsening asthma. Additionally, some patients have increased risk of bleeding and of kidney damage.

The PREVENT CLOT study protocol is the confidential intellectual property of the PREVENT CLOT Principal Investigators, Steering Committee, and the University of Maryland Baltimore and METRC and cannot be used in any form without the expressed permission of the Principal Investigators.

There is potential that patients in the aspirin arm will be at lower or higher risk relative to the patients in the LMWH arm just as there is a risk for patients in the LMWH arm to have better or worse outcomes than those in the aspirin arm. The trial is designed to assess this potential difference in risk.

A DSMB for the study will closely monitor event reporting, and should differential risks or benefits be identified, will consider stopping the study.

In this study, as with many others, there is a potential risk of breach of confidentiality, although the study team will make all reasonable efforts to mitigate this risk.

2.3.2 Potential Benefits It is not clear that one drug treatment will provide any benefit over another. Patient participants will receive \$20 as compensation for time and effort returning for the 3-month study visit.

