8.1 Definitions

8.1.1 Adverse event

Any untoward or unfavorable medical occurrence in a human subject, including abnormal sign (e.g., abnormal physical exam or laboratory finding), symptom or disease temporally associated with the subject’s participation in the study, whether or not considered related to the subject’s participation. Several adverse events, or complications, will be collected as primary and secondary outcomes of the study. The most severe of these events include: (1) Death, (2) Fatal bleeding into a critical organ (retroperitoneal, intracranial, intraocular, intraspinal); (3) Significant/massive PE central pulmonary embolism with resulting heart strain (PE); (4) Wound drainage or hematoma requiring reoperation; (5) Wound drainage, bleeding or hematoma that does not require reoperation; (6) Bleeding event that requires intervention (e.g. chest tube, interventional radiology embolization); (7) Surgical Site Infection requiring reoperation; (7/8) Surgical site infection that does not lead to reoperation but requiring antibiotic treatment; (9) Greater than 2 mg/dL drop in hemoglobin within 24 hrs; and (10) GI Bleed. These and other

The PREVENT CLOT study protocol is the confidential intellectual property of the PREVENT CLOT Principal Investigators, Steering Committee, and the University of Maryland Baltimore and METRC and cannot be used in any form without the expressed permission of the Principal Investigators.

complications common in the trauma population will be reviewed in aggregate twice annually by the DSMB to assess for differences between treatment groups. They will be reported to the IRB on an annual basis, unless they meet the criteria for Serious Adverse Event (see below).

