7.3.4 Secondary Safety Estimands

Major Bleeding Event

7. Difference (aspirin minus LMWH) in the probability of being *observed* to have a bleeding event by 90 days for eligible patients under assigned treatment, in a world without loss-to-followup;

Wound Complication

8. Difference (aspirin minus LMWH) in the probability of being *observed* to have a wound complication by 90 days for eligible patients under assigned treatment, in a world without loss-to-followup.

Deep Surgical Site Infection

9. Difference (aspirin minus LMWH) in the probability of being *observed* to have a deep surgical site infection by 90 days for eligible patients under assigned treatment, in a world without loss-to-followup;

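### GI bleeds and procedure-treated bleeds that miss the bleeding composite's criteria are listed as outcomes in section 8.1.1 but enter no estimand and no planned by-arm table

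*Combined protocol and SAP*

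**What the plan says.** Section references are to protocol version 11.0 unless stated.

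Section 8.1.1 introduces its list with "Several adverse events, or complications, will be collected as primary and secondary outcomes of the study". Among the most severe of these it gives item "6) Bleeding event that requires intervention (e.g. chest tube, interventional radiology embolization" and, as separate items, "9) Greater than 2 mg/dL drop in hemoglobin within 24 hrs; and (10) GI Bleed". Section 8.2.2.1 refers back to this list when it says that complications are classified as study outcomes.

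Section 3.3.3 defines the one bleeding outcome. Its first component is "symptomatic bleeding into a critical area or organ". The second opens with a laboratory criterion, "bleeding causing a drop in hemoglobin level of 2 g/dL or more over a 24-hour period". The transfusion alternative and the third component then read "or leading to transfusion of two or more units of whole blood or red cells or; 3) bleeding requiring reoperation". The definition has no item for GI bleeding as such and none for a non-operative procedure.

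SAP section 7.3.4 makes Estimand 7 the aspirin-minus-LMWH contrast in how likely a patient is "to have a bleeding event by 90 days for eligible patients under assigned treatment, in a world without loss-to-followup". The heading calls it a major bleeding event, and the SAP lists no components. Estimands 8 and 9 cover wound complications and deep surgical site infection. Under SAP section 7.4, Estimands 2 to 9 get 95% confidence intervals and no significance tests.

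Section 2.3.1 names "possible risk of inflammation or ulceration of the stomach" as an aspirin risk. For LMWH it names bleeding that may need transfusion or operation. Hypothesis 3 in section 3.1 expects fewer complications on aspirin.

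**The concern.** Two sections of the current protocol give different accounts of which bleeds are outcomes. Section 8.1.1 treats a GI bleed and an intervention-treated bleed as outcomes in their own right. Under section 3.3.3 they count only if they also meet a site, hemoglobin, transfusion or reoperation criterion. The rest are collected, at least in part, but never compared between arms in the planned report.

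One of the missing event types, GI bleeding, is related to a harm the protocol names for aspirin, and the safety comparison is the one in which aspirin is expected to do better. A reader of the results would want to see whether GI bleeding differs between arms. As planned, the main paper could not show this for bleeds below the composite's criteria.

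**Working it through.** **1. The sections side by side.**

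| Event | Section 8.1.1 | Section 3.3.3 composite | Estimand |
|---|---|---|---|
| GI bleed with a drop of at least 2 g/dL in 24 h, or at least 2 units | item 10 | counted (component 2 applies at any site) | 7 |
| GI bleed meeting no criterion | item 10 | not counted | none |
| Bleed treated by chest tube or embolization, meeting a criterion | item 6 | counted | 7 |
| The same, meeting no criterion | item 6 | not counted | none |
| Wound hematoma returned to surgery | item 4 | counted (component 3) | 7 and 8 |
| Wound bleeding or hematoma without reoperation, meeting no criterion | item 5 | not counted | none |

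An example of the second row is a GI bleed treated endoscopically with one unit, with hemoglobin falling evenly by 3 g/dL over three days. The fall is 3/3 = 1 g/dL per 24 h, below 2, and one unit is below two. This assumes that endoscopy is not a reoperation and that the stomach is not a critical organ (the examples in 8.1.1 item 2 do not include it). If the same fall included 2 g/dL within any 24-hour window, the bleed would count.

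**2. Other planned tables.** SAP section 6 tabulates serious adverse events, which it defines as unexpected. A GI bleed on aspirin is an anticipated risk and would normally not qualify. Protocol 8.1.3 admits expected serious events only if they are related or possibly related to the study and occur more often than expected. SAP section 2 reports complications only for late ineligibles and inappropriate enrollments. The twice-yearly DSMB review in 8.1.1 does compare the listed events between groups, but that is monitoring and not part of the reported analysis.

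**3. Collection.** CRF07 (3 months) has a GI-bleed item. CRF05 (index hospitalization) has none, only a general field for other clinically significant bleeding. The record review in section 6.2.1 also covers such bleeding.

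**4. Effect on the estimate.** Let a and l be the proportions of aspirin and LMWH patients whose only qualifying event is a bleed outside the composite's criteria. Counting them changes the aspirin-minus-LMWH difference by a − l. The documents give neither rate. A gap of 0.1 point is 0.001 × 6,100 = 6.1 patients.

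The only planning figure available is in version 1.0, section 10.1: 80% power for infection/bleeding of 10% against 8.47%, with 7.5% loss. To reproduce it, n = 6,100 × 0.925 = 5,642.5 per arm and power = Φ[(Δ − 1.96·√(2p̄(1−p̄)/n)) / √(p₁(1−p₁)/n + p₂(1−p₂)/n)]. With Δ = 0.0153 and p̄ = 0.09235, this is Φ[(0.0153 − 0.01068)/0.00545] = 80.2%. The stated figure is sound.

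As an illustration only, assumed rates are added to those two planning rates:

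| a (aspirin) | l (LMWH) | a − l, points | LMWH minus aspirin, points | Power |
|---|---|---|---|---|
| 0.1% | 0.1% | 0 | 1.53 | 79.8% |
| 0.5% | 0.5% | 0 | 1.53 | 78.3% |
| 0.2% | 0.1% | +0.10 | 1.43 | 74.0% |
| 0.5% | 0.25% | +0.25 | 1.28 | 63.6% |
| 1.0% | 0.5% | +0.50 | 1.03 | 44.6% |
| 0.1% | 0.2% | −0.10 | 1.63 | 84.4% |
| 0.25% | 0.5% | −0.25 | 1.78 | 89.4% |

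The sign of the change is the sign of a − l, so the table cannot say which row applies. The 10% rate belongs to a superseded infection/bleeding composite that may already have included these events. It is not a rate for Estimand 7.

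**5. Hemoglobin item.** Section 8.1.1 says more than 2 mg/dL; section 3.3.3 says at least 2 g/dL, which is 2,000 mg/dL. Both the unit and the inequality differ. Section 6.2.1, CRF05 and CRF07 agree with 3.3.3.

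**The case against.** The best defence is that the composite is a literature-based definition of major bleeding and is meant to leave out lesser bleeds. Its hemoglobin and transfusion criteria apply at any site and equally to both arms. That stands. A reader might infer that the endpoint omits GI bleeding altogether, and it does not. It is also a reason to leave the composite alone. It does not explain why 8.1.1 gives the left-out events outcome status and no analysis then reports them.

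A second defence concerns direction. A reader might infer that the composite captures LMWH bleeding fully and aspirin bleeding only when severe, so that the result is tilted toward aspirin. The documents do not support this. Bleeds needing a chest tube or embolization are not specific to aspirin, and section 2.1 raises concern about bleeding into critical organs with LMWH. Item 5 of 8.1.1, wound bleeding or hematoma without reoperation, also falls outside the wound endpoint. Section 2.1 reports fewer wound hematomas with aspirin in hip fracture and arthroplasty, so leaving out item 5 may hide LMWH events. An aspirin excess of GI bleeds is plausible from section 2.3.1 but not shown.

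Third, the outcome is secondary and untested, the DSMB sees the events by group, and CRF05 has a general bleeding field. These points limit the consequences and make the remedy easier, but they do not put the events into the report. A reoperated hematoma appearing under both Estimands 7 and 8 is not double counting, because the two are not summed. Version 1.0 named both event types among its complications. That version is superseded, and the change is not in itself an error.

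**Conclusion.** The point holds as an inconsistency between sections and a reporting gap. GI bleeds and procedure-treated bleeds that miss every criterion in section 3.3.3 are outcomes under section 8.1.1 but reach no estimand and no planned by-arm table. This follows from the text, given that non-operative procedures are not counted as reoperation.

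The size and direction of any effect on the aspirin-minus-LMWH difference are unknown. It equals the between-arm gap in such bleeds, which the documents do not give, and could be zero or go either way. A reader might want to express the gap as a share of the 1.53-point planned difference. That would need an assumed one-directional excess and a superseded infection/bleeding composite, so no such share can be stated.

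No formal claim is at risk, because Estimand 7 carries an interval and no test. The unknown direction is itself a reason to report these events by arm. The hemoglobin unit conflict in 8.1.1 is minor and does not affect the endpoint definition.

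**What to change.** Keep the section 3.3.3 composite as Estimand 7 and list its components in SAP section 7.3.4. Add there, by arm and with 95% confidence intervals, as descriptive estimates:

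- (a) any GI bleed;
- (b) bleeding needing any procedure, including endoscopy, embolization or chest tube;
- (c) a sensitivity version of Estimand 7 that adds (a) and (b).

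Identify in-hospital GI bleeds from the index-hospitalization record already reviewed under section 6.2.1, or from the CRF05 field for other clinically significant bleeding. Reconcile the threshold and unit in 8.1.1 item 9 with section 3.3.3 and the CRFs.

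The cost is a SAP wording change, some abstraction from records already under review, and a few extra lines in the safety table. It needs no added patients, tests or alpha. The apparent safety difference may change in either direction.

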3.3.4 Tertiary Outcomes

The following outcomes will be assessed to address the study’s secondary aims:

- Patient medication satisfaction will be measured using the Treatment Satisfaction Questionnaire for Medication (TSQM).³¹ The 14 item TSQM was developed and

The PREVENT CLOT study protocol is the confidential intellectual property of the PREVENT CLOT Principal Investigators, Steering Committee, and the University of Maryland Baltimore and METRC and cannot be used in any form without the expressed permission of the Principal Investigators.

validated by Akinson and colleagues and effectively measures patient satisfaction with various medications. TSQM domains include side effects, effectiveness, and convenience, which sum to a single measure of the patient's medication-related experience satisfaction.

- Direct out of pocket medication cost to the patients related to the blood clot medicines as reported at the final follow up visit

4. STUDY OVERVIEW

The proposed study is a pragmatic multi-center, prospective, randomized trial of 30 mg of subcutaneous low molecular weight heparin/enoxaparin (LMWH) administered twice daily versus 81 mg of enteral aspirin (ASA) taken twice daily in orthopaedic trauma patients. Treatment will be initiated during the initial hospitalization for injury, and will continue for the duration of time the patient is prescribed prophylactic clot prevention medication, per the standard of care at the treating facility. Patients will be followed for 3 months following date of randomization to the trauma center to assess for death, rehospitalization, or complication which occurred between discharge and follow up. At this time, satisfaction, adherence and out of pocket costs will also be reported.

5. STUDY POPULATION

5.1 Description of the Study Population

Approximately 12,200 participants (6,100 per treatment arm) will be enrolled from participating METRC centers over a 42-month period. Participants will be recruited as soon as the decision to place them on prophylactic clot prevention medication is made at the initial hospitalization for their injuries. Consenting procedures are described in detail in Section 6 of this protocol.

5.1.1 Participant Inclusion Criteria

1. Does the patient have a planned operative or non-operative pelvis or acetabular fracture, or any operative extremity fracture proximal to the metatarsals/carpals?
2. Is the patient at increased risk of blood clot(s) from their orthopaedic injury(ies) and will receive a prophylactic blood thinner regimen per standard of care?
3. Is the patient 18 years or older?

5.1.2 Participant Exclusion criteria

1. Did the patient present to the hospital more than 48 hours post injury?
2. Has the patient received more than 2 doses of LMWH or Aspirin for initial prophylaxis?

The PREVENT CLOT study protocol is the confidential intellectual property of the PREVENT CLOT Principal Investigators, Steering Committee, and the University of Maryland Baltimore and METRC and cannot be used in any form without the expressed permission of the Principal Investigators.

3. Is the patient on long term blood thinners (other than low-dose aspirin or platelet inhibitors such as Plavix or Aggrenox)?
4. Did the patient have a VTE within the last 6 months?
5. Is the patient on therapeutic (as opposed to prophylactic) blood thinners for an acute issue at the time of admission?
6. Does the patient have a newly diagnosed indication for therapeutic blood thinners (for example vascular injury) that will require therapeutic anticoagulation for more than one week?
7. Does the patient have an allergy to aspirin, or NSAIDs, or a history of heparin induced thrombocytopenia, or other medical contraindication to blood thinners (e.g. peptic ulceration, gastrointestinal bleeding, etc)?
8. Is the patient on higher dose aspirin (>81 mg once a day or higher) for medical reasons or will be treated with higher dose aspirin?
9. Does the patient have underlying chronic clotting disorders (i.e. Factor V Leiden, hemophilia, Protein C and S deficiency) that require full dose anticoagulation or are a contraindication to VTE chemoprophylaxis?
10. Does the patient have end stage renal disease, or impaired creatinine clearance <30 ml/min at time of randomization?
11. Is the patient pregnant or lactating?
12. Does the patient speak neither English nor Spanish?
13. Is the patient is a prisoner?
14. Is the patient is likely to have severe problems maintaining follow-up?
15. Is the patient, based upon the clinical judgment of the treating clinician, NOT equally suited for treatment with either Aspirin or Lovenox?
16. Should the patient be excluded for other reasons at the discretion of the treating physician?
17. Does the patient have a known COVID-19 diagnosis prior to fracture treatment or within 3 months of the index fracture?

Due to the acute nature of injuries experienced by the trauma patient population, some patients may have conditions or treatment plans that are unknown at the time of enrollment that, but when discovered later causes them to become ineligible. Patients who are enrolled and later meet an exclusion criterion that was present but undiagnosed at the time of enrollment will be withdrawn and considered a late ineligible participant.

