6.1.2 Consent and Enrollment

In-person consent:

Once eligibility has been confirmed, the informed consent process will be completed by the Research Coordinator and/or a clinician certified to participate in this study. Eligible study participants or their legally authorized representative (LAR) will be approached as soon as they are able to give consent, and may be enrolled in the study through the time that the first two doses of anticoagulation therapy are administered; i.e. they may receive 2 doses of SOC (as defined by the center) therapy prior to randomization and initiation of the study-directed medication. Individual sites will develop local procedures that will ensure these requirements can be met. Patients and their families may be provided with a pamphlet (Attachment C) describing

The PREVENT CLOT study protocol is the confidential intellectual property of the PREVENT CLOT Principal Investigators, Steering Committee, and the University of Maryland Baltimore and METRC and cannot be used in any form without the expressed permission of the Principal Investigators.

the study, the risks and benefits of participation and what will be expected of them if they choose to participate. A video (Attachment D) describing the study treatment and procedures may be provided to assist with the recruitment process. If a patient is unable to consent before 2 doses of SOC anticoagulation therapy are administered and there is no LAR available, the patient will not be eligible for study participation and will be recorded as such. Consent will be obtained in accordance with principles of GCP and ICH guidelines.

Tele or remote consent:

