6.2.1 Medical Record Review

For all enrolled participants, data related to the index hospitalization will be collected. This will include a daily check of the medication administration record to ensure that the patient is receiving the study drug to which he/she was assigned and to document adherence. If treatment is stopped, held or changed the research team member will either identify the reason for change from the chart or by asking the primary team if the reason is not documented. Other data to be collected includes orthopaedic and other injury characteristics, admission labs, and complications, including a fatal bleed, ≥ 2 g/dL drop in hemoglobin, reoperation for hematoma evacuation or surgical site infection, other clinically significant bleeding or infectious complication, VTE, PE, and any imaging studies (and results) conducted for bleeding or VTE concerns. Information on the administration of a limited number of concomitant medications with known potential for bleeding side effects will also be collected, including Plavix, or other platelet inhibitors, aspirin, NSAIDs (e.g. toradol, ibuprofen), and any administration of a full dose of anticoagulation medication, as well as the reason, will be recorded.

Due to the potential affects that COVID-19 has on patients, ie increased risk of clotting, COVID-19 status will be recorded if available via medical record review during the index hospitalization and at follow up. Research team member will record whether the patient is experiencing any symptoms related to COVID-19 or has tested positive. Patients who have tested positive during the index hospitalization will be excluded from the study. Patients who test positive between discharge from the index hospitalization and follow up will remain in the study with data collection of COVID-19 status in the case report form. These data will also be retrospectively collected on all patients who have enrolled into the study since January 2020.

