8.8 Replacement of a Participant Who Discontinues Study Treatment

Participants who are withdrawn from the study will not count towards the total sample size accrual and will be replaced. Participants who are lost to follow up and have unknown treatment or outcome status will be counted as lost and will not be replaced.

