3. the number of patients not enrolled and associated reasons
4. the number of enrolled and randomized patients
5. number randomized to aspirin group, number randomized to low-molecular-weight heparin (LMWH) group
6. within treatment group, the number of late ineligibles, late refusals, and inappropriate enrollments
7. within treatment group, the number initiating treatment protocol
8. within treatment group, information on 90 day follow-up (including separate metrics for key endpoints)
9. within treatment group, the number included in the per-protocol analysis

The independent adjudication committee will make the final determination on late ineligibles and inappropriate enrollments while masked to the treatment arm. Late ineligibles and inappropriate enrollments will be removed from all analyses. The outcomes, complications, adverse events of late ineligibles and inappropriate enrollments who received treatment will be reported, to the extent possible.

3 Follow-up Time

Patients were expected to return for a study follow-up visit at 90 days post admission. If participants are unable to return to the clinic, they may be contacted to complete the 90 days follow up visit via phone or email. In addition, medical record reviews will be conducted to determine whether there was documented clinical/research contact beyond the last study follow-up visit. If that visit occurred less than 90 days following randomization, the end of follow up will be defined as the last study follow-up visit or the last clinical/research contact if applicable, and follow-up time will be the duration between randomization and the end of follow up. A figure showing the distribution of follow-up time through 90 days by treatment group will be produced. Differences between treatment groups based on follow-up time through 90 days will be evaluated. Details of reasons for premature study discontinuation will be presented.

4 Baseline Characteristics

A table will report summary statistics of baseline characteristics of participants by treatment groups. Characteristics will include age, sex, body mass index, tobacco use, history of venous thromboembolism, co-morbidities, additional medications, health insurance status, injury severity score, and injury region.

5 Adherence to Treatment Protocol

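### Section 6.2.1 excludes enrolled patients on an in-hospital COVID-19 positive without limiting this to results before randomization, and exclusion criterion 17 does not say as of what date it is judged

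*Combined protocol and SAP*

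**What the plan says.** All references are to protocol version 11.0 and the SAP dated January 21, 2021.

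- **Criterion 17** (Section 5.1.2, repeated in the Protocol Summary) asks: "Does the patient have a known COVID-19 diagnosis prior to fracture treatment or within 3 months of the index fracture". It does not say at what moment the question is answered, or whether the three months run back or forward from the fracture.
- **Section 6.2.1**, on data collected for every enrolled participant, says: "Patients who have tested positive during the index hospitalization will be excluded from the study". It continues: "Patients who test positive between discharge from the index hospitalization and follow up will remain in the study". On the COVID-19 data it adds: "These data will also be retrospectively collected on all patients who have enrolled into the study since January 2020".
- **Section 6.1.2** places randomization early in the stay. Of eligible patients it says that "they may receive 2 doses of SOC (as defined by the center) therapy prior to randomization".
- **Section 5.1.2, closing paragraph**, defines late ineligibles as enrolled patients who "later meet an exclusion criterion that was present but undiagnosed at the time of enrollment will be withdrawn".
- **Section 8.8**: "Participants who are withdrawn from the study will not count towards the total sample size accrual and will be replaced".
- **SAP Section 2**: "Late ineligibles and inappropriate enrollments will be removed from all analyses". A committee masked to arm decides who belongs to these two groups, and outcomes of removed patients who received treatment are to be reported as far as possible.
- **Section 10.5.1** defines intention to treat as analysing every patient in the arm assigned by randomization.

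The SAP does not mention COVID-19.

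**The concern.** A rule that drops a patient because of something first found after randomization takes away the protection that randomization gives. Section 6.2.1 is such a rule for in-hospital positives, and the protocol itself links COVID-19 to a higher risk of clotting, so these patients may not be a random subset with respect to death. Treatment is open-label, so testing and length of stay could depend on the arm.

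The plan also leaves the handling of these patients open. Sites could withdraw and replace them, the adjudication committee could class them as inappropriate enrollments, or follow-up could stop at the positive test and the patient be censored in the Kaplan-Meier estimate. The first two routes lose the patient. The third censors on an event that may be related to death, which a Kaplan-Meier estimate assumes does not happen. If criterion 17 is also read forward, sites hold two incompatible rules for post-discharge positives.

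**Working it through.** **1. The rules by time of the COVID-19 finding**

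| Finding | Criterion 17 | Section 6.2.1 | Late ineligible (5.1.2)? |
|---|---|---|---|
| Diagnosis known before randomization | Excluded at screening if within its window | In-hospital positive excluded | Not needed |
| Infection present at enrollment, first detected later in the stay | Unclear | Excluded | Arguably yes |
| Infection acquired after randomization, detected in the stay | Excluded only if read forward | Excluded | No |
| Positive after discharge, within 3 months of fracture | Excluded only if read forward | Kept | No, if acquired after enrollment |

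The third row is the core. Section 6.2.1 divides time at discharge, not at randomization, so it excludes a patient whom no stated analysis rule covers, while Section 10.5.1 requires that patient to be analysed. In the fourth row the conflict exists only on the forward reading. The two Section 6.2.1 sentences do not conflict with each other, because they cover different periods.

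**2. The plan's own power figure**

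Inputs: 6,100 per arm, death risk 1.0% in both arms and margin 0.75% (Section 10.1); two-sided 96.2% interval, so one-sided alpha 0.019 and z = 2.075 (SAP Section 7.4). The 7.5% attrition is stated for the original design and assumed here to carry over.

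- Standard error = √(2 × 0.01 × 0.99 / 6,100) = 0.00180. Power = Φ(0.0075/0.00180 − 2.075) = 98.2%.
- With 7.5% attrition (5,642.5 per arm): 97.3%.
- Chance of declaring non-inferiority at 1.0% versus 1.75%: 1.9% at a single look.

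These agree with the stated power above 95% (Section 10.1; above 90% in SAP Section 7.3.1) and the stated error below 2.5%.

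**3. Power after removals**

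The documents give no count of positives. If an assumed 2% of the 12,400 randomized (248 patients) were removed, 6,076 per arm remain: power 98.1%, or 97.3% with attrition. Power is not the problem. The 248 would exceed the 12,400 − 12,200 = 200 patients allowed for all post-randomization removals.

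**4. Possible bias, with assumed rates only**

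Scale: 1% of 6,100 is 61 expected deaths per arm; the margin is 0.0075 × 6,100 = 45.75 deaths; one death in one arm moves the difference by 1/6,100 = 0.016 percentage points.

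Let a fraction f of each arm be removed, with death risks qA (aspirin) and qL (LMWH) among those removed and equal risk among those kept. The difference hidden is f × (qA − qL).

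- qA = qL: zero.
- f = 1%, 10% versus 5%: 0.05 points, 7% of the margin.
- f = 2%, 20% versus 5%: 0.30 points, 40% of the margin.

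If instead the true overall risk is 1% in both arms and q is common, but removal is 2% on aspirin and 1% on LMWH, the risk after removal is (0.01 − f × q)/(1 − f). With q = 10% this gives 0.816% versus 0.909%, a spurious −0.093 points (12% of the margin). Swapping the arms reverses the sign in each case.

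**The case against.** Several points on the other side stand.

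- **Criterion 17 is a present-tense screening question about a known diagnosis.** Eligibility is confirmed at randomization (Section 6.1.2), the inclusion/exclusion form is baseline only (Appendix B), and patients must present within 48 hours of injury. No diagnosis from the following three months can be known then. A reader might infer a forward window because the first half of the criterion already covers every earlier diagnosis. That reading is possible but not forced: non-operative pelvic and acetabular fractures are eligible and may lack a clear treatment date, so the fracture date may serve as an alternative anchor, or the phrase may limit the look-back. What remains is ambiguity; neighbouring criteria 4, 5 and 10 do state their time reference.
- **No sentence says COVID-19 exclusions leave the analysis.** A reader might infer that the SAP removes them. Section 6.2.1 speaks of the study, not the analysis, and an infection acquired after enrollment falls outside the late-ineligible definition. This does not clear the rule: it leaves the patient excluded with no stated analysis status.
- **Masked adjudication and reporting of removed patients' outcomes** reduce selective removal. They do not restore the randomized comparison.
- **Retrospective collection is collection only.** A reader might infer that patients enrolled since January 2020 were later removed. No document shows that.

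It can also be argued that Section 6.2.1 means tests at admission. But the section concerns enrolled participants, and its next sentence starts at discharge, so the first naturally covers the whole stay.

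**Conclusion.** The concern holds in a limited form. As written, Section 6.2.1 excludes enrolled patients on an in-hospital COVID-19 result that may arise after randomization. That does not fit the intention-to-treat definition or the late-ineligible rule, and the SAP does not settle it. Criterion 17 adds an ambiguity that becomes a contradiction only if read forward.

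The size and direction of any bias cannot be determined from the documents. Under the assumed rates above it runs from zero to 0.30 points in either direction, and it is zero if removals and risk are equal across arms. Power is essentially unchanged.

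A reader might go further and count lost deaths: 12,200/42 × 17 months gives about 4,938 patients enrolled from January 2020, and 1–4% positive with 2–10% mortality gives 1 to 20 deaths against about 122 expected. The documents supply neither rate, and this count includes post-discharge positives that Section 6.2.1 keeps, so it should not be relied on. The rule should be corrected because it is faulty as stated, not because harm has been shown.

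**What to change.** Reconcile the Protocol Summary, Sections 5.1.2 and 6.2.1, and SAP Section 2:

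1. Anchor criterion 17 to a diagnosis known at or before randomization, with the direction of any three-month window stated.
2. State in Section 6.2.1 that a positive arising only after randomization, in hospital or later, is recorded but does not remove the patient from follow-up or from the intention-to-treat set.
3. State in the SAP that such patients are neither late ineligibles nor inappropriate enrollments, and are not replaced or censored for this reason.
4. Keep in, or return to, the intention-to-treat set any patient removed solely on such a result, where 90-day status can be obtained.
5. Report exclusion of COVID-19 positives as a sensitivity analysis only.

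The wording takes a few sentences, COVID-19 status is already collected, and the sample size does not change. The real cost is in item 4: if any patients were removed, their 90-day status has to be recovered, for which Section 6.3.1 already describes record review, contact attempts and death-file searches. The clinical care of a patient who tests positive is a separate matter on which this point takes no position.
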